3.1.1 Dose Limiting Toxicity

In the Phase I portion of the study, dose limiting toxicity is defined as any of the following occurring during Cycle 1 of therapy:

- Grade 4 or greater anemia or neutropenia exceeding 5 days duration
- Thrombocytopenia requiring transfusion
- Grade 3 or greater nonhematologic toxicity possibly, probably or definitely related to the investigational therapy – excluding alopecia;

Full toxicity criteria outlined in Section 6.4.

3.1.2 Dose Escalation

3.1.2.1 Dose Escalation for MTD Determination

The doses of mithramycin which will be used at each level are indicated below, and are based on modeling performed using pharmacokinetic results obtained in our recent Phase II mithramycin trial (protocol 12C0151) and of initial patient results in this trial (16C0152). The schema of drug exposure has been selected to optimize growth inhibition and transcriptional reprogramming in clinical settings. The overall goal is to administer a dose of mithramycin during a 24-hour infusion that is equivalent to the total dose administered during 7 daily 6 hour infusions at a dose of 30-50 mcg/kg per infusion (210-350 mcg/kg) used in our recent Phase II trial (12C0151). This dose range would be expected to produce plasma levels approximating 50-100 nM by the end of infusion (**Figure 10**). The selection of only those patients with favorable ABCB4, ABCB11, RALBP and

CYP8B1 genotypes should allow more efficient escalation of mithramycin doses with acceptable toxicities.

**Dose Escalation Schema for 24h Mithramycin Infusions
(For MTD Determination in Initial Cohort 1 Arm 1 Patients)**

Dose Level	Dose (mcg/kg)
-1	30
-1A	45
1	60

The first 3 patients in Cohort 1 received mithramycin and experienced Grade 4 ALT/AST elevations. Two of these three patients continued mithramycin at a reduced dose (30 mcg/kg; DL-1) without exhibiting dose-limiting toxicity (refer to Section 1.3.4.2).

As such in Amendment E of this protocol (Version Date 11/01/2019) the dose levels have been amended and MTD determination will begin anew with 3 patients at dose level DL-1 (30 mcg/kg), to be assessed during the first treatment cycle for DLT. The MTD is the dose level at which no more than 1 of up to 6 patients experience DLT during Cycle 1 of treatment, and the dose below that at which at least 2 (of ≤ 6) patients have DLT.

If the 3 patients at DL-1 do not exhibit DLT, the next 3 patients will receive mithramycin at an increased dose of 45 mcg/kg (DL-1A) provided that at least 2 weeks have elapsed since the third patient of dose level DL-1 was treated to rule out unacceptable delayed toxicities (primarily hepatic and hematologic). Patients who receive mithramycin infusions without dose limiting toxicity (DLT) during Cycle 1 will be eligible for treatment during Cycle 2 at the same dose level in order to assess clinical as well as molecular effects of cumulative mithramycin exposures. Nausea, vomiting and diarrhea will not be considered dose limiting toxicities unless refractory to maximal standard prophylactic measures.

Dose escalation will continue at DL-1A (45 mcg/kg) as indicated above using 3 patients per dose level until DLT (assessed during the first treatment cycle) is observed. The MTD is the dose level at which no more than 1 of up to 6 patients experience DLT during Cycle 1 of treatment, and the dose below that at which at least 2 (of ≤ 6) patients have DLT. We anticipate that the MTD will be 45 mcg/kg.

If 1 of 3 patients in DL-1 experiences DLT, up to 3 additional patients will be treated at this dose level.

- If only 1 of 6 patients exhibits DLT, subsequent patients will be enrolled into DL-1A. As soon as 2 patients in a cohort at any given level develop DLT, no additional patients will be entered at that level and subsequent patients will be accrued into the preceding dose level; if DLT is observed in less than 2 of 6 patients treated at this lower level, this dose will represent maximum tolerated dose (MTD).
- If more than 1 of 6 patients experience DLT, if necessary*, 3 additional patients will be accrued to DL-1, which will be designated the MTD if fewer than 2 of 6 subjects

experience DLT. (*It may be necessary to accrue 3 additional patients to this dose level if 6 subjects have not been treated.) Accrual will continue until an MTD is determined.

Following completion of the fourth cycle of therapy, all patients will undergo evaluation consisting of physical exam, blood work, and appropriate staging studies to define response to treatment. Those individuals who exhibit disease progression will be taken off study. Patients who exhibit stabilization or regression of their disease will be eligible for 4 additional mithramycin infusions at the same dose level at which they were originally treated. Patients will continue therapy in this manner until off-study criteria have been met.

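### The MTD rule sets no minimum number treated, so 0/3 at DL-1A (45 mcg/kg) can literally satisfy it, although the rest of the plan works to six patients per level

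*Combined protocol and SAP*

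**What the plan says.** Section 3.1.2.1 gives the MTD definition in two places. Its first half reads "The MTD is the dose level at which no more than 1 of up to 6 patients experience DLT during Cycle 1 of treatment". Its second half requires the level above to have shown at least 2 DLTs in six or fewer patients.

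The dose table lists DL-1 (30 mcg/kg), DL-1A (45 mcg/kg) and level 1 (60 mcg/kg). On the patients already treated, the section says "The first 3 patients in Cohort 1 received mithramycin and experienced Grade 4 ALT/AST elevations"; Section 10 places three patients at level 1. After the amendment, "MTD determination will begin anew with 3 patients at dose level DL-1 (30 mcg/kg").

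For the step up, the text is "Dose escalation will continue at DL-1A (45 mcg/kg) as indicated above using 3 patients per dose level until DLT" is observed. It adds: "We anticipate that the MTD will be 45 mcg/kg".

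The written expansion step is "If 1 of 3 patients in DL-1 experiences DLT, up to 3 additional patients will be treated at this dose level". The bullets beneath it hold the six-patient test. Once 2 patients at any level have DLT, accrual moves to the level below, and "if DLT is observed in less than 2 of 6 patients treated at this lower level, this dose will represent maximum tolerated dose (MTD").

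Section 10 gives a Phase I maximum of 15, made up of the 3 patients already treated plus 6 each at DL-1 and DL-1A should both levels need that many.

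**The concern.** The most favourable course for the trial is 0/3 at DL-1 followed by 0/3 at DL-1A. On that course no sentence says whether patients 4 to 6 are treated at 45 mcg/kg. The explicit expansion trigger names DL-1 and needs one DLT. The six-patient test is written as a step back from a level that proved toxic. What remains is the definition, which sets only an upper limit on the number treated.

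The selected dose goes to 14 Phase II patients in stage 1. Section 10 allows up to 42 evaluable Phase II patients, or 36 new ones if 6 carry over from Phase I. The DLT rule does not follow them: "In the Phase I portion of the study, dose limiting toxicity is defined as any of the following occurring during Cycle 1 of therapy". Phase II has individual dose holds and reductions (Section 3.3) and weekly team review (Section 7.3.1), but no numerical DLT limit at cohort level. The number of patients behind the dose choice therefore matters.

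**Working it through.** **1. The plan's own figure.** Section 10's maximum is 3 already treated + 6 at DL-1 + 6 at DL-1A = 15. It reproduces, and it allows for six at DL-1A without requiring them.

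**2. Does 0/3 at DL-1A meet the definition?**
- First half: 0 DLTs is no more than 1, and 3 patients is within the ceiling of 6. Met.
- Second half: the level above DL-1A in the table is 60 mcg/kg, where 3 of 3 had Grade 4 ALT/AST elevations. Under Section 3.1.1 a related Grade 3 or higher nonhematologic toxicity in Cycle 1 is a DLT. Assuming these events were related and fell in Cycle 1, there were at least 2 DLTs. Met.

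The MTD could therefore be declared on three patients.

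**3. What three patients show.** Exact one-sided 95% upper bounds on the DLT rate:
- 0/3: 1 − 0.05^(1/3) = 0.632
- 0/6: 1 − 0.05^(1/6) = 0.393
- 1/6: the p solving (1−p)^6 + 6p(1−p)^5 = 0.05, which is 0.582

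**4. Chance of accepting DL-1A once it is reached.** Let p be the true DLT rate and q = 1 − p. Both rules below take 1/3 to expand to six.
- Three suffice after 0/3: q³ + 3pq²·q³
- Six always required: q³(q³ + 3pq²) + 3pq²·q³

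At p = 0.2, q³ = 0.512 and 3pq² = 0.384. Three suffice: 0.512 + 0.384 × 0.512 = 0.709. Six required: 0.512 × 0.896 + 0.384 × 0.512 = 0.655.

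At p = 0.4, q³ = 0.216 and 3pq² = 0.432. Three suffice: 0.216 + 0.432 × 0.216 = 0.309. Six required: 0.216 × 0.648 + 0.432 × 0.216 = 0.233.

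| Assumed DLT rate | Three suffice after 0/3 | Six required |
|---|---|---|
| 10% | 0.906 | 0.886 |
| 20% | 0.709 | 0.655 |
| 30% | 0.494 | 0.420 |
| 40% | 0.309 | 0.233 |

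The documents give no DLT rate for 45 mcg/kg on this schedule, so these rates are assumptions shown as a range.

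**5. Patients and time.** On the 0/3, 0/3 path Phase I is 3 + 3 + 3 = 9. With six at DL-1A it is 3 + 3 + 6 = 12. At Section 10's accrual of 10 to 15 a year, 3 patients take 3/15 × 12 = 2.4 to 3/10 × 12 = 3.6 months.

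**The case against.** The best answer is that the plan already intends six at DL-1A. The first bullet speaks of any level, and with 3/3 toxic at 60 mcg/kg the preceding level in the table is 45 mcg/kg, to be tested on six. The second bullet, on more than 1 of 6 with DLT and a return to DL-1, makes best sense as a step back from a six-patient DL-1A. Section 10 budgets six there, and its remark that up to 6 Phase I patients may continue into Phase II fits a six-patient MTD cohort. As evidence of intent this stands. It does not settle the text. The bullets sit under a branch that opens with one DLT at DL-1. They describe stepping down after toxicity, whereas here 45 mcg/kg is reached by escalation after a restart at 30. Section 10's six per level is conditional. If six is intended, the definition contradicts it, and that supports the correction.

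It is also fair that the effect is small. Acceptance differs by 2 to 8 percentage points over assumed rates of 10% to 40%, and the 63% bound after 0/3 is not far above the 58% after 1/6, a result that the six-patient rule accepts.

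A reader might go further and infer that, because determination began anew, the 60 mcg/kg results no longer count and 0/3 at DL-1A sends new patients back to 60. The documents do not support that. On the same assumption that the Grade 4 events were DLTs, the any-level bullet closes a level after 2 DLTs. Section 10 names only DL-1 and DL-1A as amended levels, and its 15 leaves no new places at 60. Expecting 45 to be the MTD presupposes that the level above it is toxic. Section 3.1.2.1 also refers to Section 1.3.4.2 for these patients, and that section was not in the text available for review.

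**Conclusion.** The point holds as a drafting gap of minor severity. The stated rule can select the Phase II dose on three patients, while the bullets and the sample-size budget work to six. The consequence is an upper bound of 63% rather than 39% after a clean cohort, and an acceptance probability higher by about 0.05 at a true DLT rate of 20% and by about 0.08 at 40%.

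This rests on three assumptions: that the 60 mcg/kg events were related and in Cycle 1, that 1/3 at DL-1A would expand to six, and that DL-1A is reached. It is not a finding that Phase II lacks safety monitoring, nor that the protocol directs new patients to 60 mcg/kg.

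**What to change.** In both definitions, replace the ceiling with a fixed denominator: *1 or fewer of 6 patients*. Add one sentence: after 0/3 or 1/3 at DL-1A, the level is expanded to six DLT-evaluable patients before it is declared the MTD. For clarity, a further line could say that 60 mcg/kg is closed to new patients and that its three patients supply the at-least-2-DLT half of the definition, unless Section 1.3.4.2 already says so.

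The cost is wording, up to 3 more patients at DL-1A (9 to 12 on the 0/3, 0/3 path, within the stated 15), about 2.4 to 3.6 months of accrual, and one more Cycle 1 observation period before Phase II opens. A dose with a true 10% DLT rate would be accepted 89% rather than 91% of the time, a small price for using the plan's own six-patient standard throughout.

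### At DL-1, the restart dose and lowest level, the rule for two or more DLTs points to a dose level that does not exist, no outcome without an MTD is stated, and the Phase I maximum is 54 in section 2.4 but 15 in section 10.

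*Combined protocol and SAP*

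**What the plan says.** The table in section 3.1.2.1 lists three levels: -1 (30 mcg/kg), -1A (45 mcg/kg) and 1 (60 mcg/kg). Since Amendment E, MTD determination restarts with 3 patients at DL-1. The reason is stated: "The first 3 patients in Cohort 1 received mithramycin and experienced Grade 4 ALT/AST elevations". Section 10 places those 3 patients at DL1.

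The instructions that bear on failure at DL-1 are:

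- For one DLT: "If 1 of 3 patients in DL-1 experiences DLT, up to 3 additional patients will be treated at this dose level".
- In the first bullet below that sentence, once two patients at any level have a DLT: "no additional patients will be entered at that level and subsequent patients will be accrued into the preceding dose level".
- In the second bullet, when more than 1 of 6 have a DLT: "3 additional patients will be accrued to DL-1, which will be designated the MTD if fewer than 2 of 6 subjects" experience DLT. Its footnote adds: "It may be necessary to accrue 3 additional patients to this dose level if 6 subjects have not been treated".
- The closing sentence: "Accrual will continue until an MTD is determined".

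The MTD is defined as a level with at most 1 DLT in up to 6 patients, lying below a level with at least 2. Section 3.1.2.2 opens Phase II only after an MTD has been defined.

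On numbers, section 2.4 allows as many as 54 Cohort 1 patients in Arm 1 before the MTD is known. Section 10 gives a Phase I maximum of 15, uses 15 again in its accrual forecast, and sets a ceiling of 60 for the whole study.

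**The concern.** The MTD is a primary objective and Phase II depends on it. The first dose tested after a restart prompted by toxicity is the one place where the de-escalation rule has no destination. If DL-1 fails, the reader is told to close it, to move to a level that is not in the table, and to go on accruing until an MTD is found. No sentence says that Phase I ends without an MTD.

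The second bullet does not fill the gap. It sits under the DL-1 branch, but it names DL-1 as the place to add patients, which makes sense only if the failure was at DL-1A.

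The cap printed beside the words about determining the MTD, 54, is 3.6 times the number in section 10 (54 / 15), so it does not bound an open-ended Phase I in any useful way.

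**Working it through.** **Step 1. Follow each DL-1 result through section 3.1.2.1.**

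| Result at DL-1 | Next step in the text | Executable? |
|---|---|---|
| 0 of 3 with DLT | Go to DL-1A | Yes |
| 1 of 3, then 0 of the next 3 | Go to DL-1A | Yes |
| 2 or more of up to 6 on the first pass | Close DL-1, move to the preceding level | No: none exists |
| 0 of 3, DL-1A fails, DL-1 filled to 6, 2 or more DLTs | Same closing rule | No: none exists |

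**Step 2. Test the second bullet under both readings.** Suppose its trigger is DL-1. If more patients are added, they go to a level just closed. If 6 have already been treated, the footnote leaves nobody to add and the condition of fewer than 2 DLTs in 6 has already failed. Now suppose its trigger is DL-1A. Then DL-1 is filled to 6 if only 3 were treated there, and it becomes the MTD if fewer than 2 of 6 have a DLT. Only the second reading works, and section 10's count agrees with it (Step 3).

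**Step 3. Reproduce the plan's Phase I maximum.** Section 10 counts 6 patients at each of DL-1 and DL-1A plus the 3 already enrolled at DL1: 6 + 6 + 3 = 15. This reproduces exactly. The figure of 54 cannot be derived from the current levels.

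**Step 4. Check both figures against the ceiling of 60.** Section 10 gives 42 evaluable Phase II patients at most, or 36 if 6 Phase I patients carry over. Stage 1 needs 7 + 7 = 14, or 14 - 6 = 8 with the same carry-over.

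| Phase I | Phase II part | Total | Against 60 |
|---|---|---|---|
| 54 | none | 54 | 6 places left |
| 54 | Stage 1, 6 carried over (8) | 62 | 2 over |
| 54 | Stage 1, none carried over (14) | 68 | 8 over |
| 15 | full, 6 carried over (36) | 51 | 9 places left |
| 15 | full, none carried over (42) | 57 | 3 places left |

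**Step 5. Chance of reaching the undefined branch on the first pass.** Let p be the true DLT probability at DL-1. The documents do not give it, so the values below are assumptions.

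P(2 or more DLTs) = [3p²(1-p) + p³] + 3p(1-p)² × [1 - (1-p)³]

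The first term is 2 or 3 DLTs among the first 3 patients. The second is exactly 1 among the first 3 and at least 1 among the next 3.

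| p | First term | Second term | Total |
|---|---|---|---|
| 0.05 | 0.0073 | 0.0193 | 0.027 |
| 0.10 | 0.0280 | 0.0659 | 0.094 |
| 0.20 | 0.1040 | 0.1874 | 0.291 |
| 0.30 | 0.2160 | 0.2897 | 0.506 |

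The last row of the Step 1 table is not included, so these totals are slightly low.

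**Step 6. What the documents say about p.** The evidence points both ways.

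- *Reassuring:* two of the first three patients went on at 30 mcg/kg without DLT; in 12C0151 (section 1.3.4.1), four patients tolerated 30 mcg/kg per infusion; and section 3.1.2.1 says "We anticipate that the MTD will be 45 mcg/kg".
- *Limits:* the two patients were re-dosed after a first dose at another level. Zero DLTs in 2 is compatible with a true rate up to 1 - √0.05, about 78% (one-sided 95% bound). The four in 12C0151 were on a schedule of seven daily 6-hour infusions and were the patients without hepatotoxicity; the other eight of 12 had dose-limiting transaminitis at 25 mcg/kg per infusion.
- *Not relied on:* section 1.3.4.2, cited for the 30 mcg/kg experience, was not in the text available, so its detail cannot be judged.

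**The case against.** The strongest reply is that the outcome is already fixed by the rules taken together. Two DLTs close DL-1, a level with two DLTs cannot meet the MTD definition, DL-1A is reachable only after 0 of 3 or 1 of 6 DLTs, and Phase II waits for an MTD. The study has also met failure at its starting level before and handled it by amendment. Weekly team review of toxicity (section 7.3.1) makes unnoticed continued accrual unlikely. This stands as far as it goes: patients are not clearly directed to a failed dose. What it leaves open is the end of Phase I. The text says accrual continues. Neither the weekly review nor the investigator's power to end the study (section 3.6.2, an off-study criterion) is a stopping rule.

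Three further points have some force:

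- Indentation may have been lost when the text was read from PDF, so the second bullet may be better placed on the printed page. The missing level below DL-1 and the missing outcome do not depend on layout.
- The 3% to 51% range is the chance of reaching the branch under assumed rates. It does not measure harm to patients.
- The 54 is permissive, and the ceiling of 60 limits the total regardless. It still contradicts section 10. The 15 is itself a theoretical need with no allowance for patients who cannot be assessed for DLT; any replacement has to come from the 3 to 9 places left under 60.

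**Conclusion.** The concern holds and should be fixed. The de-escalation rule cannot be completed at the restart dose, and no outcome without an MTD is written down; both follow from the text with no assumption. How often this would matter depends on an unknown DLT rate: about 3% at a true rate of 5%, rising to about 51% at 30%. The consequence is an ambiguous end to Phase I and not a clear instruction to expose more patients to a failed dose.

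The conflict between 54 and 15 also needs no assumption. Only 15 follows from the current dose levels, and 54 cannot coexist with the ceiling of 60 once Phase II Stage 1 is added.

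**What to change.** Make three wording changes:

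1. **Section 3.1.2.1, second bullet.** Tie it to DL-1A: if 2 or more of up to 6 patients at DL-1A have a DLT, fill DL-1 to 6 when only 3 have been treated there, and declare DL-1 the MTD if fewer than 2 of the 6 have a DLT.
2. **Section 3.1.2.1, failure at DL-1.** Add that if 2 or more patients at DL-1 have a DLT, including while DL-1 is being filled to 6, accrual stops, no MTD is declared, and Phase II stays closed unless an amendment adds a lower dose level. Qualify the closing sentence about continued accrual to match.
3. **Section 2.4.** Replace 54 with 15 to agree with section 10.

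The cost is a protocol wording amendment. It adds no patients or procedures, and section 10's Phase I maximum of 15 and the ceiling of 60 do not change.

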3.1.2.2 After MTD Has Been Defined

Once the MTD has been defined, an additional 14 patients (7 with primary thoracic malignancies and 7 with neoplasms of non-thoracic origin metastatic to the chest) will initially be enrolled in a Phase II setting, to more fully evaluate clinical and molecular responses at the MTD (Phase II – Simon Stage 1). If one or more patients exhibit response to therapy, 14 additional patients will be accrued to the respective cohort(s) to more fully assess clinical efficacy of the four cycle treatment regimen (Phase II-Simon Stage 2).

Patients will be closely monitored for the development of toxicities using regular physical examinations, blood pressure monitoring, and laboratory evaluations with particular attention to the development of any signs of hepatotoxicity or bleeding. Patients will be hospitalized in the NIH Clinical Center during the infusion. Following each course of therapy (four 14-day cycles) patients will undergo appropriate staging studies to determine response to therapy using RECIST criteria.

3.2 DRUG ADMINISTRATION

Given our recent findings within our recent Phase II mithramycin trial (12C0151) pertaining to ABCB4, ABCB11, RALBP and CYP8B1 SNPs that distinguish patients who did and did not experience mithramycin-mediated hepatotoxicity, this protocol will accrue only those patients with favorable ABCB4/ABCB11/RALBP/CYP8B1 genotypes.

Mithramycin will be administered intravenously via central line over 24 hours once every 14 days (+7 days/-3 days). 12 mg IV of dexamethasone will be administered one hour prior to each infusion. Four cycles will constitute one course. Intravenous hydration will be provided as clinically indicated.

3.3 DOSING DELAYS AND MODIFICATIONS

Dose adjustments will be made according to the guidelines below, with dose levels defined as follows:

Summary of dose holding/interruptions and dose de-escalation recommendations for mithramycin in case of mithramycin -related adverse events (graded according to NCI-CTCAEv5.0)

Reduction to the next lower dose as indicated in the table in Section [3.1.2](#).

General Adverse Events	Action
Non-hematological, Grade 1 or 2 (excluding hemorrhage)	
 • Continue mithramycin therapy at full dose prescribed dose. • Apply maximum supportive care recommendations. • If prolonged duration of Grade 2 adverse event (≥ 7 days) is affecting quality of life, start the next treatment cycle at 1 dose level lower. • If event persists and continues to affect quality of life for ≥ 7 more days following initial dose reduction, start the next treatment cycle at an additional dose level lower. • If events continue to persist, discontinue drug.
Grade 3 ALT and AST	
 • Hold mithramycin therapy until recovery to Grade ≤ 1 (up to 21 days of start of cycle). • If ALT and AST resolve to Grade ≤ 1 within 21 days, maintain current dose level. • If ALT and AST do NOT resolve to Grade ≤ 1 within 21 days, dose reduce 1 level. • If Grade 3 ALT or AST occur in a subsequent cycle, dose reduce 1 level independent of the date of resolution.
Grade 4 ALT and AST	
 • Hold mithramycin therapy until recovery to Grade ≤ 1 (up to 21 days of start of cycle). • If ALT and AST resolve to Grade ≤ 1 within 21 days, reduce 1 level. • If Grade 4 ALT or AST occur in a subsequent cycle, dose reduce 1 level independent of the date of resolution.
Non-hematological, Grade 3 or 4 (excluding ALT, AST, hemorrhage and QT prolongation)	
 • Apply maximum supportive care recommendations. Hold mithramycin therapy until recovery to Grade ≤ 1 (up to 21 days from start of cycle) and start the next treatment cycle at the next lower dose level. • If recurrence of adverse event after drug hold/interruptions is observed at the reduced dose, and maximum supportive care measures applied, hold drug once again until recovery to Grade ≤ 1 (up to 21 days) and start the next treatment cycle 1 dose level lower. Note: If patient's toxicity recovers to Grade ≤ 1 prior to Day 7 of treatment cycle, dosing for that cycle may resume 1 dose level lower. • If symptoms continue to persist at Grade 3 or 4, following a maximum of 2 dose reductions, discontinue drug.
QT prolongation, Grade 3 or 4	
 • Cardiology consultation will be obtained to determine whether any cardiac functional assessment is warranted or if therapy should be delayed or discontinued. When warranted, ECGs will subsequently be reviewed by the NCI consulting cardiologist. • If therapy is continued, dose reduce 1 level for Grade 4 events.
Bleeding Events (hemorrhage)	

General Adverse Events	Action
Grade 1 events	
 Continue mithramycin therapy at full dose prescribed. Apply maximum supportive care recommendations.
Grade 2 events	
 Apply maximum supportive care recommendations. Hold mithramycin therapy until recovery to Grade \leq 1 (up to 21 days from start of treatment cycle) and start the next treatment cycle at 1 dose level lower. If recurrence of adverse event after drug hold/ interruptions is observed, and maximum supportive care measures applied, hold drug once again until recovery to Grade \leq 1 (up to 21 days from start of treatment cycle) and start the next treatment cycle at 1 additional dose level lower. If symptoms continue to persist at any grade, discontinue drug.
Grade 3 events	
 Discontinue mithramycin
Grade 4 events	
 Discontinue mithramycin

All Grade 2-4 hemorrhage events will initiate full hematologic evaluations as indicated in Section 3.5.1-Coagulation Studies, as well as formal Hematology consult.
	
Hematological Adverse Events	
Grades 1 and 2 events	
 Continue mithramycin therapy at full dose prescribed. Apply maximum supportive care recommendations.
Grade 3 events	
 Apply supportive care If toxicities resolved to allow retreatment by Day 14, resume at current dose. If toxicities resolve between Days 14-21 to allow retreatment (See Section 3.4), resume at 1 dose level lower. Following dose reduction, if toxicities persist and do not allow treatment at Day 15, but are sufficiently resolved to allow retreatment by Day 21, resume at 1 additional dose level lower.
Grade 4 events	
 Apply maximum supportive care recommendations. Hold mithramycin therapy until patient meets hematologic criteria for retreatment (see Section 3.4) (must be within 21 days of start of treatment cycle) and start the next treatment cycle at 1 dose level lower. If recurrence of hematological adverse event after drug hold/ interruptions is observed with treatment at 1 dose level lower, in the setting of maximum supportive care measures applied, hold drug once again until patient meets hematologic criteria for retreatment (see Section 3.4) (must be within 28 days of start of treatment cycle) and start the next treatment cycle at 1 additional dose level lower. If symptoms continue to persist at any grade, discontinue drug.

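### Section 3.3 directs dose reductions that the amended dose table cannot supply: only one is possible from 45 mcg/kg and none from 30 mcg/kg

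*Combined protocol and SAP*

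**What the plan says.** Section 3.3 opens with "Dose adjustments will be made according to the guidelines below, with dose levels defined as follows" and then points to a single source for the lower dose: "Reduction to the next lower dose as indicated in the table in Section" 3.1.2. The table there is captioned "For MTD Determination in Initial Cohort 1 Arm 1 Patients" and holds three levels: DL-1 (30 mcg/kg), DL-1A (45 mcg/kg) and DL1 (60 mcg/kg).

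In Section 3.3, the rows for prolonged Grade 2 non-hematological events, Grade 3-4 non-hematological events, Grade 2 hemorrhage, and Grade 3 and Grade 4 hematological events each direct a first reduction and then a second one. The Grade 3-4 non-hematological row ends with "following a maximum of 2 dose reductions, discontinue drug". The Grade 4 ALT/AST row orders one level down after recovery and adds: "If Grade 4 ALT or AST occur in a subsequent cycle, dose reduce 1 level independent of the date of resolution". The Grade 3 ALT/AST row has a similar recurrence instruction. For Grade 4 QT prolongation, one level down is ordered if therapy continues.

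Under Section 3.1.2.1, MTD determination restarts at 30 mcg/kg, the lowest level in the table. The same section says "We anticipate that the MTD will be 45 mcg/kg".

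**The concern.** Section 3.3 describes more downward steps than the amended table contains. A patient at 30 mcg/kg has nowhere to go, and a patient at 45 mcg/kg has one step. The gap includes transaminase elevation, the toxicity that led to the restart: the first three patients, enrolled at DL1, all had Grade 4 ALT/AST elevations.

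Where a reduction is ordered and no lower level exists, the treating team could stop the drug, retreat at the same dose or use an unlisted dose. Section 3.3 does not say which. The reading chosen affects safety. It also bears on the Phase II endpoint, because Section 10.2 ties response evaluability to a full four-cycle course, and the Section 10 decision rules turn on 0 versus 1 response in 7 and 2 versus 3 in 21.

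**Working it through.** **Inputs.** Listed levels {30, 45, 60} mcg/kg, from Section 3.1.2.1. Reductions directed per row, from Section 3.3.

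**Formula.** Steps available from a dose = number of listed levels below it. Shortfall = steps directed − steps available, where positive.

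- From 60: levels 45 and 30, so 2 steps.
- From 45: level 30, so 1 step.
- From 30: no level, so 0 steps.

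**The plan's own figure.** The stated maximum of 2 reductions can be reached only from 60 mcg/kg. Section 10 does not plan further patients there: its Phase I maximum of 15 is 6 at DL-1 + 6 at DL-1A + the 3 already enrolled at DL1.

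| Row in Section 3.3 | Steps directed | From 60 | From 45 | From 30 |
|---|---|---|---|---|
| Prolonged Grade 2 non-hematological | 2 | fits | short by 1 | short by 2 |
| Grade 3-4 non-hematological | 2 | fits | short by 1 | short by 2 |
| Grade 2 hemorrhage | 2 | fits | short by 1 | short by 2 |
| Grade 3 hematological | 2 | fits | short by 1 | short by 2 |
| Grade 4 hematological | 2 | fits | short by 1 | short by 2 |
| Grade 4 ALT/AST: first event plus one recurrence | 2, no limit stated | fits | short by 1 | short by 2 |
| Grade 3 ALT/AST: unresolved at 21 days plus one recurrence | 2, no limit stated | fits | short by 1 | short by 2 |
| Grade 4 QT, if therapy continues | 1 | fits | fits | short by 1 |

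One qualification applies to the Grade 3 ALT/AST row. If the first event resolves within 21 days the dose is kept, and a recurrence then orders a first reduction, which is available from 45.

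**Does another section supply the answer?** Take a patient at 30 mcg/kg with Grade 4 ALT/AST that recovers to Grade 1 or less within 21 days.

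- Section 3.3 orders one level down. None is listed.
- Section 3.4 allows continued treatment while the drug is tolerated as Section 3.3 defines it, and allows a next course at the same or a reduced level. A recovered patient can meet its laboratory conditions, so it does not force removal.
- Section 3.6.1 removes patients for excessive toxicity as Section 3.3 defines it, but the ALT/AST rows contain no discontinuation step.
- Section 3.1.2.1 allows Cycle 2 at the same dose for patients without DLT in Cycle 1. It sets no general rule for patients with DLT, although it reports that two of the first three patients did continue, at 30 mcg/kg.

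Sections 3.4 and 3.6.1 therefore lead back to Section 3.3, which gives no executable instruction for this patient.

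**The case against.** The strongest reply is that this is narrow and that the plan has backstops. Much of that stands.

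- **Backstops.** Failing the Section 3.4 conditions, which include the eligibility laboratory limits for a next course, is a removal criterion, as is the patient's best interest. These cover toxicity that does not resolve. They do not settle toxicity that recovers at 30 mcg/kg.
- **A ceiling is not a promise.** The maximum of two reductions is an upper limit, so having one step does not by itself contradict it. That is right, but the preceding bullet in that row still directs a second reduction.
- **Wording.** The table title calls its contents recommendations, so calling the reductions mandatory would be strong. The lead-in and the rows are nevertheless directive.

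A reader might also infer more than the documents support:

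- **That all 42 Phase II patients are affected.** That figure is the evaluable maximum (2 × 21). At 45 mcg/kg the first step, to 30, works, so only patients who need a second one meet the gap. If 30 became the MTD, the gap would arise at the first reduction.
- **That reductions are the expected case**, because 8 of 12 patients (67%) in the predecessor trial had dose-limiting transaminitis. That trial gave seven daily 6-hour infusions, before genotype selection. The three Grade 4 cases here were at DL1, and the two who continued at 30 mcg/kg did so without DLT. Reductions are foreseeable, but no rate is known at 30 or 45.
- **That different sites will act differently.** Infusions are given at one centre, and Section 7.3.1 has the team discuss each patient weekly.

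**Conclusion.** The point holds in limited form and should be fixed. From 45 mcg/kg, all five two-step rows lack a target for the second reduction, as does a second ALT/AST reduction. From 30 mcg/kg, every reduction lacks a target, including the single QT step. This applies both to patients who start at 30 and to those who reach it from 45. The number of patients affected, and any effect on the response endpoint, cannot be estimated from the documents.

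The conclusion assumes that the Section 3.1.2 table is the only list of dose levels. The lead-in to Section 3.3 announces dose levels, but none follow in the text available for this review. If a separate list stands there in the source file, the count should be repeated against it. The cross-reference to Section 3.1.2 makes that less likely.

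**What to change.** The sponsor should reconcile Section 3.3 with the amended table in Section 3.1.2 on three points:

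1. For each row that orders a reduction, state one outcome for a patient already at the lowest listed level.
2. Make the number of reductions described fit the steps available from each starting level.
3. Give the ALT/AST rows a stated endpoint.

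Which outcome applies is a clinical choice for the sponsor, and none is proposed here. The cost is amendment wording in one table. The small downside is that the text would show fewer available reductions than Section 3.3 now describes.
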